1 BACKGROUND AND RATIONALE

1.1 Scientific rationale for investigation of losmapimod in COVID-19

COVID-19 is a severe pandemic disease with high mortality particularly in older individuals, due to infection with the SARS-CoV-2 coronavirus. The therapeutic hypothesis for the use of losmapimod in COVID-19 disease is that increased mortality and severe disease is caused by p38 mitogen-activated protein kinase (MAPK)-mediated exaggerated acute inflammatory response resulting from SARS-CoV-2 infection. The older population is especially at risk of severe disease and death upon infection with SARS-CoV-2. The hyperactivated immune response in COVID-19 shares features of the cytokine storm syndrome and appears to be responsible for the severe pulmonary edema, ARDS, and cardiac and renal disease responsible for most of the severe morbidity and mortality.

The proposal to develop losmapimod, a potent, specific, and bioavailable p38 α/β inhibitor, for treatment of COVID-19 is based on the following rationale:

- (1) Nonclinical work has shown that older mice infected with SARS-CoV-1 develop much more severe disease than younger ones, and that treatment with a p38 MAPK small molecule inhibitor greatly reduced their mortality when given after viral inoculation; similar survival benefit of p38 MAPK inhibition has been seen in animal models of severe H5N1 influenza and HSV-1.
- (2) Nonclinical work has shown that p38 MAPK inhibition reduces viral load in several experimental models with coronaviruses, including mouse hepatitis virus, human CoV-229E, transmissible gastroenteritis virus, and Middle East respiratory syndrome virus.
- (3) p38 MAPK is proposed to play a critical role in the development of ARDS, including regulating the expression and activity of inflammatory mediators such as ICAM-1, HMGB1, and ET-1, neutrophil chemotaxis and apoptosis, the balance of Treg/Th17 cells, and pulmonary endothelial cell apoptosis.
- (4) Clinical investigation showing that excessive acute inflammation in response to external stressors in older individuals, including viral antigen challenges, hinders the specific immune response to infection; many of the excessive inflammatory mediators associated with this aberrant immune response in older individuals are associated with activation of the p38 MAPK pathway.
- (5) Treatment with losmapimod in older subjects restored the normal immune response to viral antigen challenge and improved the resolution of acute inflammation.
- (6) Treatment of various inflammatory diseases with losmapimod, including active rheumatoid arthritis (RA), acute myocardial infarction, and chronic obstructive pulmonary disease (COPD) resulted in significant reduction in markers of acute inflammation, including interleukin-6 (IL-6), C-reactive protein (CRP), chemokines such as CXCL13, and other markers (see [Table 5](#) for further details).
- (7) Losmapimod may be beneficial in COVID-19 treatment via reduction of the damaging effects of angiotensin II (Ang II). Angiotensin-converting enzyme 2 (ACE2) is the cellular receptor for SARS-CoV viruses and is expressed in the lung and the heart. Upon infection with SARS-CoV-2, there is internalization of and depletion of ACE2. ACE2 converts Ang II into angiotensin 1-7 (Ang 1-7), which counterbalances the vasoconstrictive and pro-inflammatory effects of Ang II. Ang II is significantly elevated in COVID-19, and the levels are positively correlated with viral load and acute lung injury ([Liu Y et al, 2020](#)). Blocking the p38 MAPK pathway in nonclinical models has been

Fulcrum Therapeutics
Protocol FIS-001-2020

Losmapimod

shown to reduce many of the adverse effects of elevated Ang II, resulting in lower frequency of cardiac arrhythmias, renal failure, and hypertension.

p38 inhibitors have been explored extensively in clinical trials for numerous chronic inflammatory indications, as summarized in the [Investigator Brochure](#). Losmapimod has been extensively tested in humans and found to be generally well tolerated, including in over 3600 adult healthy volunteers and subjects in 11 different indications. The 15 mg oral (PO) twice per day (BID) dose proposed for the COVID-19 Phase 3 study has been shown to provide robust and sustained inhibition of the p38 MAPK pathway systemically and in tissues, specifically in skeletal muscle needle biopsies of subjects with facioscapulohumeral muscular dystrophy (FSHD). This dose of losmapimod was shown experimentally in older (median 69 years, range: 65, 77 years) human volunteers to restore the normal immune response to viral challenge and improve the resolution of acute inflammation. Furthermore, losmapimod has been shown to significantly reduce markers of hyperactive acute innate immune inflammation in the context of acute myocardial infection, RA, and COPD in clinical trials as listed below:

- 1- Single-dose study in 50 subjects with RA (RA 3103730). Treatment with losmapimod (N=38) reduced levels of IL-6 compared with placebo (N=12). Losmapimod was dosed as follows: 7.5 mg: 13 subjects; 20 mg: 12 subjects; 60 mg: 13 subjects. Analysis of serum IL-6 at 3 hours post dose showed significantly lower levels with losmapimod than with placebo ([Table 2](#)).

Table 2: Change from Baseline in IL-6 Serum Levels with Increasing Single Doses of Losmapimod in Subjects with Rheumatoid Arthritis

Treatment group	Adjusted ratio to baseline	95% CI	Adjusted ratio to placebo	95% CI
Placebo	0.92	0.60, 1.41		
Losmapimod 7.5 mg	0.41	0.26, 0.63	0.45	0.24, 0.82
Losmapimod 20 mg	0.43	0.27, 0.68	0.47	0.25, 0.88
Losmapimod 60 mg	0.38	0.25, 0.57	0.41	0.23, 0.75

Abbreviations: CI = confidence interval.

- 2- Repeated-dose study in subjects with acute coronary syndrome (ACS; PM1111810). A total of 535 subjects with non-ST elevation myocardial infarction were randomized to an initial dose of 7.5 or 15 mg of losmapimod followed by 7.5 mg PO BID (N= 388) or matching placebo (N=138) for 12 weeks. Results showed that relative to placebo, losmapimod significantly suppressed CRP and IL-6 acutely at the 24- to 36-hour assessments ([Table 3](#)).

Table 3: Change from Baseline in hsCRP and IL-6 with 7.5mg PO BID Losmapimod Over Placebo in Subjects with Acute Coronary Syndrome

Parameter	Placebo (N=138)	All losmapimod (N=388)	P value
hsCRP at 72 hours or discharge (nmol/L)	110.8 (83.1-147.7)	64.1 (53.0-77.6)	<0.05
IL-6 at 24 hours (ng/L)	10.6 (8.6-13.1)	6.6 (5.8-7.4)	<0.05

Abbreviations: hsCRP = high-sensitivity C-reactive protein; IL-6 = interleukin-6.

- 3- Repeated-dose study in subjects with COPD (MK1113006). In this study, subjects with COPD were dosed with losmapimod 2.5 mg BID (N=149), losmapimod 7.5 mg BID (N=151), or placebo BID (N=154) for 24 weeks; or losmapimod 7.5 mg BID for 4 weeks followed by losmapimod 15 mg BID (N=150) for 20 weeks. Over the first 12 weeks of treatment, statistically significant reductions in serum high-sensitivity CRP (hsCRP) levels were observed in the losmapimod 7.5 mg and 15 mg groups compared with placebo. For hsCRP, Week 12, 7.5 mg dose versus placebo: ratio 0.73; 95% confidence interval [CI] 0.57, 0.93;

Fulcrum Therapeutics
Protocol FIS-001-2020

Losmapimod

p=0.011; 15 mg dose versus placebo: ratio 0.64; 95% CI 0.50, 0.82; p<0.001. [Table 4](#) shows the results for the subgroup with higher CRP at baseline.

Losmapimod is a highly selective p38 inhibitor at advanced stage of clinical development with excellent safety data profile	
 Losmapimod Investigator Brochure Fulcrum 2020 Cadavid D et al. FSHD IRC Poster. 2019

Abbreviations: BID = twice daily; COVID-19 = disease caused by novel coronavirus; IND = investigational new drug application; SARS-CoV-1 = severe acute respiratory syndrome coronavirus 1; SARS-CoV-2 = severe acute respiratory syndrome coronavirus 2.

Fulcrum Therapeutics
Protocol FIS-001-2020

Losmapimod

1.2 Benefit-risk considerations

This is the first-in-human clinical trial with losmapimod for the treatment of a novel virus (COVID-19) and, therefore, the risk-benefit considerations are based on nonclinical data in conditions related to COVID-19 (e.g., SARS-CoV-1) as well as extensive clinical data in other inflammatory conditions and conditions involving the p38 MAPK pathway (e.g., FSHD, RA, COPD) including in older healthy volunteers; refer to [Section 1.1](#) for further details.

Losmapimod has been found to be generally well tolerated in clinical trials, including in over 3600 adult healthy volunteers and subjects in 11 different indications. The 15 mg PO BID dose proposed for this study has been shown to provide robust and sustained inhibition of the p38 MAPK pathway systemically and in tissues, specifically in skeletal muscle needle biopsies of subjects with FSHD.

Complete clinical safety data and nonclinical data for losmapimod can be found in the [Investigator's Brochure](#). Additional adverse events not previously observed in animals or in humans may also occur in this trial. Subjects in this clinical trial will be monitored closely for the development of adverse effects that may result from study drug administration. In addition, a Data Monitoring Committee (DMC) will monitor the safety of subjects throughout the study on an ongoing basis.

COVID-19 is a severe and rapidly progressive infection, especially in the high-risk population (ie, older, with comorbidities) selected for this trial. Given the extensive clinical experience with losmapimod, the potential benefit of losmapimod treatment in this indication outweighs the risks.

2 STUDY OBJECTIVES AND ENDPOINTS

All study objectives will be evaluated in subjects diagnosed with COVID-19.

Objectives	Endpoints
Primary	
To assess the efficacy of losmapimod compared with placebo for treatment of COVID-19 when administered concurrently with standard of care	Proportion of progressors to death or respiratory failure by Day 28
Secondary	
To evaluate the effect of losmapimod compared with placebo on clinical outcomes	
Clinical status by Days 7 and 14 as measured on the 9-point WHO ordinal scale (WHO 2020):
 
• (8) death• (7) ventilation plus additional organ support (vasopressors, renal replacement therapy, ECMO)• (6) Intubation and mechanical ventilation• (5) noninvasive ventilation or high-flow oxygen therapy• (4) oxygen therapy but not requiring high-flow or non-invasive ventilation• (3) hospitalized but not requiring oxygen therapy• (2) Discharged from the hospital but with limitation of activities• (1) Discharged from the hospital and without any limitation• (0) No clinical evidence of the disease
To assess the effect on clinical status of treatment with losmapimod compared with placebo	
Total number of study days free of oxygen supplementation by Day 28
 
Total number of study days in ICU by Day 28
 
Total number of study days hospitalized by Day 28
 
Total number of respiratory failure-free study days by Day 28

Fulcrum Therapeutics
Protocol FIS-001-2020

Losmapimod

Objectives	Endpoints
	Percentage of subjects discharged from the hospital by Day 28
To assess the effect on survival following treatment with losmapimod compared with placebo	All-cause mortality at Day 28 Number of study days alive by Day 28
To assess the safety and tolerability of losmapimod compared with placebo	Incidence of AEs and SAEs Incidence of clinically significant changes in laboratory parameters and vital sign measurements
To characterize changes in SARS-CoV-2 infection following treatment with losmapimod compared with placebo	Quantifiable viral RNA on Day 7

Abbreviations: AE = adverse event; [REDACTED]; ALT = alanine aminotransferase; AST = aspartate aminotransferase; COVID-19 = disease caused by novel coronavirus; CRP = C-reactive protein; ECG = electrocardiogram; ECMO = extracorporeal membrane oxygenation; [REDACTED]; ICU = intensive care unit; IL-6 = interleukin-6; [REDACTED]; PD = pharmacodynamics; RNA = ribonucleic acid; SAE = serious adverse event; SARS-CoV-2 = severe acute respiratory syndrome coronavirus 2; WHO = World Health Organization.

Fulcrum Therapeutics
Protocol FIS-001-2020

Losmapimod

3 STUDY IMPLEMENTATION

3.1 Overall study design and plan

This Phase 3 multicenter, randomized, double-blind, placebo-controlled study will evaluate the safety and efficacy of losmapimod versus placebo on a background of standard of care in subjects with COVID-19 disease.

This study will be performed in hospitalized subjects ≥ 40 years old, who have a C-reactive protein (CRP) >15 mg/L, who have been diagnosed with COVID-19, and who can undergo randomization within 7 days of collection of the sample found positive for the SARS-CoV-2 virus and before progressing into critical disease. Critical disease is defined as cardiac failure, septic shock, or ARDS or immediate need for intubation or mechanical ventilation per the judgment of the investigator.

Subjects who sign informed consent (refer to [Section 9.1.3](#)) and meet all entry criteria (see [Section 4](#)) may be enrolled.

Up to 410 subjects will participate for a maximum of 34 days, divided as follows:

- Screening: Day -3 until Day -1 before the first study drug administration.
- Treatment period of 14 days:
 - Subjects randomized (1:1) to either:
 - losmapimod tablets 15 mg PO BID; OR
 - matching placebo tablets PO BID
 - Randomization will be stratified by age (<65 or ≥ 65) and requirement for oxygen at randomization (yes/no)
- Follow-up: 7 (± 3) days after last dose and 14 (± 3) days after last dose.

The first 10 enrolled subjects (approximately 5 placebo and 5 losmapimod) will be dosed and followed for at least 72 hours after their first dose for an interim "sentinel" safety review before any additional subjects are dosed. Dosing of additional subjects will continue if there are no drug-related safety concerns from the initial subjects dosed as assessed by an independent DMC. The DMC will review safety data for the sentinel subjects and all subjects at regular intervals throughout the study as outlined in the charter (see [Section 8.10](#)).

The Sponsor will monitor individual adverse events (AEs) and toxicities on an ongoing basis throughout the study.

See [Table 1](#) for the time points of the assessments.

All study visits during the first week of treatment are anticipated to be conducted in the inpatient setting. If the clinical status of the subject improves such that the clinician discharges the subject from the hospital before the end of the study, the follow-up assessments will be conducted on an outpatient basis by alternative methods, including the use of local laboratories/facilities or home visits for blood draws, telemedicine, and/or outpatient follow-up clinic visits as deemed clinically appropriate per COVID-19 follow-up standard of care (SOC) at each site (refer to [Section 6.7](#)).

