Percentage of subjects discharged from the hospital by Day 28: percentages of subjects discharged from the hospital will be tabulated by treatment arm, along with differences between treatment arms. The proportion of subjects will be compared using an adjusted risk difference obtained from a regression model, adjusting for stratification factors, sex, and baseline CRP. Full details of the regression model will be provided in the SAP.

All-cause mortality at Day 28: percentages of subjects will be tabulated by treatment arm, along with differences between treatment arms, at each time point. The proportion of subjects will be compared using an adjusted risk difference obtained from a regression model, adjusting for stratification factors, sex, and baseline CRP. Full details of the regression model will be provided in the SAP.

Incidence of AEs/SAEs: will be summarized by system organ class and preferred term and by treatment arm using percentages.

Incidence of clinically significant changes: Percentage of subjects with clinically significant changes in laboratory parameters, ECG, and vital sign measurements will be computed for each treatment arm along with associated 2-sided 95% Clopper-Pearson CI.

Clearance of quantifiable viral RNA by Day 7: percentages of subjects with clearance of quantifiable viral RNA will be tabulated by treatment arm, along with differences between treatment arms, at each time point. The proportion of subjects will be compared using an adjusted risk difference obtained from a regression model, adjusting for stratification factors, sex, and baseline CRP. Full details of the regression model will be provided in the SAP.

Table 1: Visit and Assessment Schedule

Assessment ¹	SCR Time point -3d to -1d	Treatment Period												FU ¹⁴		ET
		D1 (base- line)	D2	D3	D4	D5	D6	D7	D8	D10	D12	D14	D21 (± 3d)	D28 (± 3d)		
Informed consent	X															
Demography	X															
Inclusion and exclusion criteria	X	X														
Medical history	X															
COVID-19 history and clinical diagnosis ²	X															
Chest X-ray/CT scan	X ³	X ³														
Study drug administration:																
Randomization		X														
Losmapimod or placebo PO BID		X	X	X	X	X	X	X	X	X	X	X				
Pharmacodynamics:																
Drug levels/PK ⁴		P, 4-5h	4-5h	4-5h	4-5h	4-5h	4-5h	4-5h					4-5h		X	
Clinical status and symptoms:																
Respiratory failure and survival assessment ⁶		X	X	X	X	X	X	X	X	X	X	X	X	X	X	

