3.4.2 Subject withdrawal

Subjects may withdraw from the study at any time and for any reason without prejudice to their future medical care by the investigator or at the study site. In all cases of impending consent withdrawal, investigators will be given instructions to meet and discuss with the participant their options of continuing in the study. The investigator should ensure understanding and documentation of the reasons for the participant's desire to withdraw consent. Every effort should be made to keep subjects in the study, including if a subject and/or their treating physician decides to prematurely discontinue study treatment. Unless the participant provides their written withdrawal of consent or there is other written documentation by the investigator confirming the participant's verbal intent to completely withdraw from the trial, participants should be followed for all protocol-specified evaluations and assessments. The reasons for subjects not completing the study will be recorded.

A subject may be withdrawn from the study if he or she is lost to follow-up. For subjects to be considered as lost to follow-up, 2 attempts should be made to contact the subject to return for the scheduled study visit. After 2 attempts, a certified letter should be sent to the subject's address requesting the subject to contact the investigator to schedule a follow-up assessment. If no reply is provided by the subject within 30 days of receipt of the certified letter, the subject can then be considered lost to follow-up.

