6.3.1 Respiratory failure and survival assessment

Total number of study days free of oxygen supplementation and total number of study days free of respiratory failure will be evaluated. Refer to [Section 6.5.1](#) for further details of vital sign collection.

- Note: Respiratory failure is defined as either need for mechanical ventilation (invasive or non-invasive) or high flow oxygen (defined by greater than 15 LPM flow of oxygen to maintain oxygen saturation between 90% and 95%), sustained for at least 48 hours, at any time during the study.

The reason for hospitalization and number of total study days of hospitalization and intensive care unit (ICU) utilization will be recorded.

Details of subject discharge (date of discharge and condition at discharge) from the hospital will be recorded.

Any significant deviation from standard of care due to limited resources will be documented.

Survival status at the end of the study period will be documented, including cause of death for any reason.

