6.6.1 Early termination visit

When the investigator determines that study treatment will no longer be used, the investigator will perform the ET procedures and document the reason for discontinuation from study treatment in the eCRF. If routine laboratory tests (eg, hematology, serum chemistry) are completed within 7 days before the time of study treatment discontinuation, these tests need not be repeated. Every effort should be made to keep subjects in the study, including if a subject and/or their treating physician decides to prematurely discontinue study treatment.

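### Follow-up visits are timed from the last dose in the text but by study day in Table 1, and the closing visit may fall on Day 25 for a primary endpoint that runs to Day 28

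*Protocol*

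**What the plan says.** The primary endpoint is "Proportion of progressors to death or respiratory failure by Day 28" (Protocol section 2). Respiratory failure must be "sustained for at least 48 hours, at any time during the study" (section 6.3.1, repeated in SAP 3.4.1.1).

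The timing of the last visits is described in two ways:

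- **From the last dose.** Protocol 3.1, the synopsis and SAP 2.2.1: "Follow-up: 7 (± 3) days after last dose and 14 (± 3) days after last dose".
- **By study day.** Table 1 has follow-up columns for Days 21 and 28, each ±3 days, and marks the row "Respiratory failure and survival assessment" in both. It has a separate early-termination column.

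Other passages bear on which timing applies:

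- Section 3.1 sends the reader to Table 1 "for the time points of the assessments", and section 6 does the same. SAP 2.2.1 repeats the last-dose bullet without that pointer.
- Section 3.4.2 says that, short of complete withdrawal, "participants should be followed for all protocol-specified evaluations and assessments".
- Section 6.6.1: "When the investigator determines that study treatment will no longer be used, the investigator will perform the ET procedures". It then asks that such subjects be kept in the study, but does not say when their later visits fall.
- Section 7.1.1 collects adverse events up to the Day 28 visit.
- SAP 3.1.1 counts days from the first dose. SAP 3.1.8 multiply imputes the primary endpoint for subjects who leave early other than by death, or whose status cannot be established.

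**The concern.** A binary endpoint with a fixed horizon needs every subject's status known at that horizon. Two features of the text work against this.

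First, for anyone who stops drug before Day 14, the phrase "days after last dose" and Table 1 give different final visits. Early stopping is foreseen: section 3.4.1 lists liver and QTcF triggers, and SAP 3.3.8 has an exposure category under 7 days. A site working from the narrative text could close follow-up too soon in a selected group.

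Second, and regardless of when drug was stopped, the Day 28 visit may be held on Day 25. Such a subject has attended the last visit and has not left early, so the imputation rule need not apply. Protocol 8.4 defines completion by the last pharmacodynamic assessment, not by known status at Day 28. An event on Days 26 to 28 could then go unrecorded and the subject be scored as event-free.

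**Working it through.** **1. Where the two timings agree.** Inputs: 14 treatment days and visits 7 and 14 days after the last dose (section 3.1). Last dose on Day 14: 14 + 7 = 21 and 14 + 14 = 28, which are Table 1's days. The stated maximum of 34 days is also reproduced: 3 (screening) + 14 (treatment) + 14 (follow-up) + 3 (window) = 34. The last-dose bullet therefore describes a full course correctly.

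**2. Where they differ.** Final visit under the last-dose wording = last-dose day + 14, ±3. Days left before Day 28 = 28 − that day.

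| Last dose | Final visit, last-dose wording | Days short of Day 28 | Final visit, Table 1 |
|---|---|---|---|
| Day 2 | 16 (13–19) | 9–15 | 28 (25–31) |
| Day 4 | 18 (15–21) | 7–13 | 28 (25–31) |
| Day 7 | 21 (18–24) | 4–10 | 28 (25–31) |
| Day 10 | 24 (21–27) | 1–7 | 28 (25–31) |
| Day 14 | 28 (25–31) | 0–3 | 28 (25–31) |

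The third column applies only if a site follows the narrative wording instead of Table 1.

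**3. The window on the Day 28 visit.** Earliest permitted visit: 28 − 3 = Day 25. Unobserved: 28 − 25 = 3 days (Days 26, 27 and 28). The 48-hour requirement adds to this: at a Day 25 visit, an episode that began after Day 25 − 2 = Day 23 cannot yet have qualified. This holds for all subjects, full course or not.

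**4. The planned power, and what lost events would do to it.** Inputs from Protocol 8.1.1 and 8.6: 205 per arm, 0.30 against 0.18, one-sided 2.5%. Fixed-design formula:

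power = Φ{[δ√n − z√(2p̄(1 − p̄))] / √(p₁(1 − p₁) + p₂(1 − p₂))}

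With δ = 0.12, n = 205, p̄ = 0.24 and z = 1.96, this is Φ{[1.718 − 1.184] / 0.598} = Φ(0.894) = 81.4%. With the futility look at 103 per arm and the Table 6 boundaries (unpooled variance), power is 80.2%, so the plan's figure of about 80% is reproduced.

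The documents give neither an early-stopping rate nor the share of events falling late. As an assumption only, let a fraction f of events be missed equally in both arms, so that both rates are multiplied by (1 − f):

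| f (assumed) | Fixed-design power |
|---|---|
| 0 | 81.4% |
| 1% | 80.9% |
| 2% | 80.4% |
| 5% | 78.8% |
| 10% | 75.9% |

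The sample size does not change under the proposed fix, because Table 1 already schedules visits to Day 28.

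**The case against.** The strongest reply is that the plan, read as a whole, already follows everyone to Day 28. The last-dose bullet is an overview of the full course. Section 3.1 itself defers to Table 1, sections 3.4.2 and 6.6.1 keep subjects in the study after they stop drug, and adverse events, which include deaths, are collected up to the Day 28 visit. Subjects who leave early are imputed, and SAP 3.4.2 adds survival-type sensitivity analyses that allow for differing follow-up. A ±3-day window applies equally to both blinded arms.

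Most of this stands, and it rules out three stronger readings that a reader might infer:

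- **That early stoppers finish before Day 28 and their late events are lost.** The better reading of the documents is the opposite.
- **That the risk window runs to Day 31.** Protocol 8.1.1 and SAP 2.2.4 equate the end of study with Day 28, SAP 3.4.1.1 limits the endpoint to Day 28, and days count from first dose. The phrase about any time during the study sits inside that limit.
- **That subjects who leave the study early are scored as non-events.** The SAP treats them as missing and imputes them.

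Two things are not answered. No passage states that Table 1 takes precedence, and section 3.4.2 does not decide the matter because both timings are written into the protocol. And section 7.1.1 runs to the Day 28 visit, not to Day 28, so it does not close the gap after a Day 25 visit. Survival status is recorded at the end of the study period, but no passage requires confirmed status on or after Day 28 before a subject is scored as event-free.

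**Conclusion.** The point holds in a limited form. The timing text in Protocol 3.1, the synopsis and SAP 2.2.1 conflicts with Table 1 for anyone whose last dose is before Day 14, and the passages must be reconciled. The weight of the documents favours follow-up to Day 28, so no loss of early stoppers is shown. Separately, the ±3-day window lets a completed subject go unobserved for up to 3 of the 28 days and still be scored as a non-event.

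The size cannot be estimated: it depends on how many final visits are held early and how many first events fall on Days 26 to 28, and neither figure is given. It is probably small, since the window gap covers at most three late days. A difference between arms is possible in principle, but nothing in the documents supports asserting one. The power figures under assumed losses are illustrations, not forecasts. This is a cheap improvement to the completeness of the primary endpoint, not a must-fix.

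**What to change.** 1. In Protocol 3.1, the synopsis and SAP 2.2.1, replace the last-dose timing with Table 1's visits on Days 21 and 28 counted from first dose, whenever study drug was stopped. In section 6.6.1, add that the early-termination procedures do not replace these visits.
2. Require survival and respiratory-failure status to be ascertained on or after Day 28, with a window of 0/+3 days for this item only. Allow a telephone call or record check. Other Day 28 assessments can keep ±3 days.
3. In section 6.3.1 and SAP 3.4.1.1, state that only events with onset on or before Day 28 count. Say also how the 48 hours are confirmed for an episode that begins at the end: onset on Day 28 is confirmed on Day 28 + 2 = Day 30, which lies inside the +3 window.

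The cost is wording in two documents and a later or additional contact for some subjects. Table 1 and sections 3.1 and 6.7 already provide for telemedicine and other remote follow-up. Sample size, boundaries and the analysis model are unchanged.
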